1.5. Data analysis

Statistical analyses will be performed using XLSTAT (Addinsoft, France). Normality of continuous variables will be checked through the Kolmogorov-Smirnov test. Two-way ANOVA tests will be used to check for the effect of type of bread (2 conditions: with/without gluten) and the effect of spread (3 conditions: no spread, butter and mayonnaise) on number of chews, number of swallows, eating duration and bolus properties (saliva content). Interactions between bread and spread will be included in the analysis/model. A post-hoc test will be used for evaluating differences between values. A *p*-value lower than 0.05 will be considered statistically significant, but notable trends will also be reported and discussed. Correlation coefficients (*r*) will be calculated to explore the correlation between oral processing parameters (number of chews, number of swallows, eating duration), bread texture (hardness) and bolus properties (saliva content).

For the CATA test, frequency of mention for each term will be determined by counting the number of participants that used that term to describe each sample. Cochran's Q test will be carried out for each of the terms to detect differences in participants' perception of the evaluated samples.

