1.1. Subjects

A total of 20 subjects were recruited for this study (9 male, 11 female, average age: 34 ± 10 years). Participants were students and staff members of the Department of Agricultural, Food, Environmental and Animal Sciences at Udine University, Italy. The inclusion criteria were: age between 18-59 years old, good general oral health (self-reported), normal smell and taste functions (self-reported), absence of mastication and/or swallowing problems, normal body mass index (BMI 18.5-24.9 kg/m²) (based on self-reported weight and height) and absence of any food allergy or intolerance for gluten. All participants gave written informed consent. The study was approved by the ethical committee of the University of Udine (protocol number: 0002491).

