1.2. Bread products

A 2x3 full factorial design was used with 2 white sandwich breads (a regular gluten-containing (GC) and a gluten-free version (GF)) and 3 spread conditions (no spread, butter and mayonnaise). The breads were commercial products kindly provided by Barilla (Parma, Italy) and Nove Alpi (Pistoia, Italy). The composition of each bread is listed in table 1.

Table 1. Ingredients and nutritional information of studied gluten-free and gluten-containing bread available on the package.

Bread	Ingredients	Energy (kcal)	Total fat (g)	Saturated fat (g)	Total carbo hydrates (g)	Sugar (g)	Fibre (g)	Protein (g)	Salt (g)
Gluten-containing	Wheat flour type "0" (70.6%), water, extra virgin olive oil (2.4%), yeast, salt, sugar, malted barley flour	272	3.9	0.6	48.4	7.3	4.5	8.5	1.25
Gluten-free	Water, corn starch, rice flour, high oleic sunflower oil, yeast, dextrose, thickeners: guar-hydroxypropylmethyl cellulose, iodized salt, soy protein, rice protein, psyllium fiber, quinoa flour, corn flour, aroma	247	5.0	0.55	44.5	3.5	6.0	3.0	1.4

Bread samples were served as two stacked cylinders resembling the consumption of a sandwich (diameter: 3.5 cm, approximate total height: 2.4 cm) (Figure 1). Due to differences in bread density, the average weight of two stacked cylinders was 5.1 ± 0.2 and 5.7 ± 0.4 for GC and GF breads, respectively.

Butter (composition in 100 g: Energy: 751 kcal, Total fat: 83 g, saturated fat: 59 g, total carbohydrates: <0.5 g, sugar: <0.5 g, protein: 0.6 g, salt: <0.01 g) and mayonnaise (composition in 100 mL: Energy: 614 kcal, total fat: 68 g, saturated fat: 8.1 g, total carbohydrates: 0.6 g, sugar: <0.5 g, protein: 0.8 g, salt: 1.1 g) were added to breads at approximately 12% w/w. These spreads were selected due to the different impact they were expected to have on assisting bolus formation. Butter, a fat based product (water in oil emulsion), was expected to increase the degree of lubrication while mayonnaise, an oil-in-water emulsion, was expected to increase lubrication and moisture content of the food bolus.

[figure not shown]

Figure 1. Sample configuration: A. two stacked cylinders of bread without spread. B. two stacked cylinders of bread with spread (either butter or mayonnaise).

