1.3.1. Video recording

A digital camera (Logitech C920 PRO HD webcam, resolution 1080p/30fps) was positioned approximately 50 cm from the participant's face. Participants evaluated a total of 7 samples from which the first was a test sample used to familiarize the participants with the procedure. Samples were served in randomized order. Participants were instructed to place the whole sample in the mouth (e.g. single bite) and to chew naturally until the bolus was ready for swallowing. Participants were asked to maintain the head straight to the camera, and not to block their mouth or face with their hand while eating. Between samples, participants rinsed the mouth with water.

Videos were decoded using the behavioral annotation software ELAN (version 4.9.1; Max Planck Institute for Psycholinguistics). A coding scheme was developed (Forde et al., 2013; Bolhuis et al., 2014) to record the frequency counts of chews and swallows. Measures of total eating duration (s) (i.e. starting from the moment the sample was placed in the mouth until the final swallow) were directly extracted from the videos. Coding was done by two researchers working independently.

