1.3.2. Check-all-that-apply (CATA) test and bolus collection

During the second session, participants evaluated again the samples (n = 7): a test sample used for familiarization followed by the 6 evaluated samples in randomized order. Participants were instructed to

place the whole sample in the mouth and to chew naturally. After 5 chewing cycles, participants were asked to check all the attributes that describe the texture sensations perceived in the beginning of mastication. A list with attributes and their definitions were provided to guide the participants (Table 2). Participants could also indicate texture attributes not listed. Participants proceeded with chewing until the swallowing point, where they checked again all the attributes that characterize the texture sensations perceived at the end of mastication. The food bolus was then spat in a container, which was kept close to prevent water evaporation. Between samples, participants rinsed the mouth with water.

Table 2: Texture attributes and definitions used for the CATA test.

Attribute	Definition
Hard	Sensation that describes the resistance to being deformed by teeth during chewing.
Soft	The bread has a tender texture, easy to crush when chewing.
Compact/dense	The bread has a tight or little porous structure
Spongy	The bread has a light and porous structure
Crumbly	The bread is easy to disaggregate in crumbs and breaks down rapidly
Pasty	Sensation that describes the formation of a dough of the bolus
Dry	Sensation that describes the absence of moisture in mouth when chewing and the difficulty to moisturize the bread
Sticky/Adhesive	Sensation that describes the adhesion of the bolus to teeth and oral cavity during chewing
Sandy	Sensation that describes the presence of particles in oral cavity which tend to scratch the tongue and throat

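### The two-way ANOVA has no participant term although all 20 people eat all 6 samples, so run as written its p-values are miscalibrated

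*Combined protocol and SAP*

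**What the plan says.** Section 1.1 gives the sample: "A total of 20 subjects were recruited for this study". Section 1.2 gives the structure: "A 2x3 full factorial design was used with 2 white sandwich breads" and three spread conditions, hence six products.

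Both sessions are fully crossed within person. For the video session, section 1.3.1 says "Participants evaluated a total of 7 samples from which the first was a test sample used to familiarize the participants with the procedure", which leaves six analysed samples each. For the bolus session, section 1.3.2 says "a test sample used for familiarization followed by the 6 evaluated samples in randomized order".

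Section 1.5 then gives the model for the continuous outcomes: "Two-way ANOVA tests will be used to check for the effect of type of bread (2 conditions: with/without gluten) and the effect of spread". It adds "Interactions between bread and spread will be included in the analysis/model" and "A post-hoc test will be used for evaluating differences between values". No section mentions a participant factor, block, random effect, repeated-measures structure or sphericity correction.

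For the CATA terms, the same section says that Cochran's "Q test will be carried out for each of the terms to detect differences in" perception of the samples. That is a matched-samples test. The continuous outcomes are given no matched counterpart.

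**The concern.** People are likely to differ in how much they chew, how long they take and how much saliva they produce, whatever the bread. In a crossed design those differences cancel out of every comparison between products. An ANOVA with only bread, spread and their interaction leaves them in the error term and counts 120 values as independent.

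The distortion is not the same for every effect. If people differ mainly in overall level, all the tests are too conservative: real effects are missed, or reported only as trends, which section 1.5 allows. If people also differ enough in their response to gluten-free bread, the bread test becomes too liberal while spread and interaction in the same table stay conservative. Section 1.3 identifies the gluten-free versus gluten-containing comparison as the study's objective, so the effect whose direction of error is uncertain is the one that matters most. The post-hoc test inherits the same error term if it is taken from this ANOVA.

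**Working it through.** The plan states no power or error-rate figure, so there is none to reproduce.

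**Inputs from the documents.** 20 participants (1.1); 2 breads × 3 spreads (1.2); six analysed samples per person per session (1.3.1, 1.3.2); significance level 0.05 (1.5).

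**Assumptions.** Normal, complete data; total variance 1; variance components participant vP, participant × bread vPB, participant × spread vPS and residual vE. The documents give no SD, correlation or effect size.

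**Degrees of freedom.** Observations: 20 × 6 = 120. Error as written: 120 − 6 = 114. With an additive participant block: 114 − 19 = 95. That splits into participant × bread 19, participant × spread 38 and participant × bread × spread 38.

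**Expected mean squares with no true effect.**
- Pooled 114-df error: vP + vPB + vPS + vE
- Bread: vE + 3vPB
- Spread: vE + 2vPS
- Interaction: vE

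Setting numerator equal to error, bread breaks even at vPB = (vP + vPS)/2 and spread at vPS = vP + vPB. In this variance structure the interaction test is conservative whenever vP, vPB or vPS is above zero.

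**Hand check, level differences only, correlation 0.5 (vP = vE = 0.5), bread effect 0.4.**
- True SE of the bread difference: √(2 × 0.5/60) = 0.129
- SE assumed by the written model: √(2 × 1/60) = 0.183
- Written test rejects beyond 1.981 × 0.183 = 0.362. Power ≈ Φ((0.4 − 0.362)/0.129) ≈ 62%.
- Repeated-measures test (19 df) rejects beyond about 2.093 × 0.129 = 0.270. Power ≈ Φ((0.4 − 0.270)/0.129) ≈ 84%.

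**Simulation (40,000 trials per scenario): bread test, level differences only.**

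| Correlation | Type I error as written | Power for 0.4 SD, as written | Power for 0.4 SD, repeated measures |
|---|---|---|---|
| 0.3 | 2.0% | 60% | 70% |
| 0.5 | 0.7% | 62% | 84% |
| 0.7 | 0.1% | – | – |

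In p-value terms, the written SE is too large by 1/√(1 − ρ). By normal approximation, a result whose correct p is 0.05 would be reported as about 0.10, 0.17 or 0.28 at ρ = 0.3, 0.5 or 0.7.

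**Bread type I error when people also differ in response to bread (vPS = 0).** The numerator-to-error ratio is (vE + 3vPB)/1.

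| vP, vPB, vE | Ratio | As written | Participant block only | Repeated measures |
|---|---|---|---|---|
| 0.5, 0.1, 0.4 | 0.7 | 2.3% | 11.1% | 5.0% |
| 0.4, 0.2, 0.4 | 1.0 | 5.5% | 15.8% | 5.2% |
| 0.2, 0.3, 0.5 | 1.4 | 9.9% | 17.3% | 5.1% |

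In the last row, the written ANOVA tests spread and interaction at about 0.3%. Across 13 null scenarios, all with at least 30% of variance between people, the interaction test ran at 0.01% to 1.6%.

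**Post-hoc, one gluten-containing versus gluten-free pair within a spread, correlation 0.5, unadjusted.** Type I error is 0.8% with the 114-df error against 5.1% paired. Power for 0.6 SD is 46% against 72%.

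**The case against.** The strongest reply is that section 1.5 is brief rather than wrong. It never says the 120 values are independent, a repeated-measures ANOVA with two within-person factors is also two-way, and the choice of Cochran's Q suggests that the authors knew the samples were matched. That intention is possible, but it is not written down, and intention alone does not settle the model: adding only a participant block is a natural reading, and it inflates the bread test in the scenarios above.

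A second reply is that the likely error is conservative, so positive findings would stand. Conservative is indeed the likelier direction. The inflated bread test needs vPB above (vP + vPS)/2, which nothing in the documents supports or excludes. Lost power still matters with 20 people.

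A third is that the scenarios favour large distortion. This stands in part. At a correlation of 0.2 with level differences only, the type I errors are between about 2.5% and 3%. With vP 0.1 and vPB 0.05 they are 5.0% for bread, 3.0% for spread and 3.1% for interaction. The interaction statement also depends on the assumed variance structure, and the simulations ignore that swallows are counts.

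Finally, the plan names no primary endpoint or confirmatory hypothesis, which lowers the stakes but does not make the p-values right.

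**Conclusion.** The concern holds. The design is fully within-participant, the stated terms omit the participant, and no other section supplies the missing structure. Run as written, the bread, spread, interaction and post-hoc tests do not have their nominal error rate, except without within-person correlation or, for a main effect, near a coincidental break-even. Neither can be presumed for chewing, eating time or saliva.

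The size depends on variances the plan does not give. Lost power is the main expected harm, about 10 points at a correlation of 0.3 and 22 points at 0.5 for a 0.4 SD bread effect. A false gluten effect is a conditional risk that needs large person-to-person variation in the response to bread. Because one sentence governs the ANOVA for all four outcomes, it must be corrected before the data are analysed.

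**What to change.** In section 1.5, specify a two-way repeated-measures ANOVA with bread and spread as within-participant factors. Test bread against participant × bread (19 df), spread against participant × spread (38 df) and the interaction against participant × bread × spread (38 df), with a sphericity correction for the last two. The bread test then equals a paired t-test on each participant's two bread means.

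A linear mixed model with random participant, participant × bread and participant × spread terms and small-sample degrees of freedom is an acceptable alternative. A random intercept alone is not. Base post-hoc comparisons on the matching within-participant error; the multiplicity method, a related but separate gap, should be named in the same edit.

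The cost is wording only, with the same people and measurements. There are fewer error degrees of freedom. If participant-by-factor variation is absent, power is 3 to 4 points below that of an additive participant block (84% versus 87% at correlation 0.5; 70% versus 74% at 0.3). Where response to bread varies strongly (vP 0.2, vPB 0.3), power for 0.4 SD is 42% against 57% for the written test, but there the written test has 9.9% type I error.

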1.3. Test Sessions

Participants attended 2 sessions of approximately 30 min each. The first session was designed for video recording and the second session for the evaluation of texture attributes and collection of food bolus. Participants received detailed information about the test procedure but they were not informed that the objective of the study was to compare GF and GC breads. The sessions were carried out in a sensory room at 20 °C and under normal light conditions.

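### The texture (CATA) analysis has only a six-sample Cochran's Q per term, which cannot attribute a difference to gluten-free versus gluten-containing bread

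*Combined protocol and SAP*

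**What the plan says.** Section 1.2 sets the structure: "A 2x3 full factorial design was used with 2 white sandwich breads", crossed with three spread conditions. It also gives a reason to expect spread effects: "These spreads were selected due to the different impact they were expected to have on assisting bolus formation". The only statement of purpose is in section 1.3, in a sentence about what participants were not told: "the objective of the study was to compare GF and GC breads".

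Section 1.3.2 describes the CATA session as "a test sample used for familiarization followed by the 6 evaluated samples in randomized order". Terms are ticked after five chews and then a second time: "Participants proceeded with chewing until the swallowing point, where they checked again all the attributes". Table 2 lists nine terms.

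Section 1.5 treats the two kinds of outcome differently.

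- **Chews, swallows, eating duration, saliva content:** two-way ANOVA with bread and spread as factors, and "Interactions between bread and spread will be included in the analysis/model".
- **CATA:** "frequency of mention for each term will be determined by counting the number of participants that used that term to describe each sample", followed by "Cochran's Q test will be carried out for each of the terms to detect differences in participants' perception of the evaluated samples".

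One sentence on post-hoc testing appears in the ANOVA paragraph, before CATA is introduced. It names no test.

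**The concern.** The six samples are two breads by three spreads, yet the only CATA test treats them as six unrelated products. A significant Q says that at least one sample differs from another. It does not say whether the bread, the spread or a particular combination is responsible. Because the spreads were chosen to act differently in the mouth, a Q driven by spread alone is a realistic outcome.

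If the plan is followed as written, any statement that GF bread feels drier, crumblier or stickier than GC bread would rest on reading a frequency table by eye. Whether a spread narrows or widens such a difference would also go untested.

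**Working it through.** The plan gives no power or error-rate figure for CATA, so there is nothing of its own to reproduce.

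**Inputs from the documents:** n = 20 participants (1.1); k = 6 samples, each tasted by every participant (1.3.2); 2 breads x 3 spreads (1.2); significance level 0.05 (1.5).

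**Step 1: degrees of freedom.** Q over six samples has k − 1 = 5 df. In a 2x3 design these are bread (1) + spread (2) + interaction (2) = 5. Q pools all three.

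**Step 2: same Q, different answer on bread.** With sample totals C, participant totals r and grand total N,

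Q = (k − 1)(k ΣC² − N²) / (kN − Σr²).

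Let each of the 20 participants tick the term for 3 of the 6 samples. Then N = 60 and Σr² = 20 × 9 = 180.

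| Labelling | GC totals | GF totals | GC vs GF (of 60 each) |
|---|---|---|---|
| A | 15, 10, 5 | 15, 10, 5 | 30 vs 30 |
| B | 5, 5, 10 | 10, 15, 15 | 20 vs 40 |

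In both rows ΣC² = 2 × (225 + 100 + 25) = 700, so Q = 5 × (6 × 700 − 60²) / (6 × 60 − 180) = 5 × 600 / 180 = 16.67. On 5 df, p = 0.0052. Row B is row A with the sample labels moved. Relabelling never changes Q, so this step needs no assumption about rates of use.

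**Step 3: how often this would matter.** The documents give no rates of term use, so all rates here are assumptions. Each scenario has 20,000 simulated studies of 20 x 6 yes/no answers, with a participant effect of SD 1 on the logit scale (range for SD 0.5 to 2 in brackets where available) and unadjusted 0.05. The bread test is a paired t test on each participant's GF-minus-GC count. The interaction test is a Friedman-type chi-square (2 df) on the three GF-minus-GC differences.

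| Assumed truth | Q significant | Bread test significant |
|---|---|---|
| No effect, 45% use | 5.0% | 5.2% |
| Spread only: 64% without spread, 29% with | 89% (84–96%) | 5% |
| Bread only: 38% vs 58% in every spread | 40% (35–52%) | 64% (59–76%) |
| One GF sample at 75%, the rest at 38% | 73% (67–85%) | 31% (29–40%) |

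In the last row the interaction test rejects in 45% (40–56%). A milder spread-only effect (50% without spread, 30% with), simulated with a probit participant effect of SD 0 to 1, gives Q 31–45% and the bread test 5%.

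**Step 4: number of tests.** Nine terms at one time point, or 18 over two, give a chance of at least one false positive of 1 − 0.95⁹ = 37% or 1 − 0.95¹⁸ = 60% per factor, if the tests were independent. Under Benjamini-Hochberg control over 18 tests, with 2, 6 or 12 real effects of 38% vs 58%, power per term is 25%, 32% or 44% for the bread test and 9%, 11% or 15% for Q.

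**The case against.** The strongest reply is that Q does exactly what section 1.5 says it is for, which is to detect differences among samples. Nothing in the plan says a significant Q will be read as a bread effect. That is right: the test is valid and the gap is an omitted analysis. But the omission leaves the bread question without any CATA test.

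The post-hoc sentence might be stretched to cover CATA. Even then the test is unnamed, and pairwise comparisons (15 pairs of six samples per term) would give neither a bread main-effect test nor an interaction test.

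The objective is mentioned only in passing, the text supplied ranks no endpoints, and bread is tested for four other outcomes. So the gap is confined to texture perception. This limits its weight but does not remove it.

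The simulated rates are invented, and a smaller spread effect triggers Q less often. Nor does power settle the choice, because Q does better when a single sample stands out. Both points stand. The case rests on attribution (steps 1 and 2), and step 3 only illustrates size.

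Finally, sections 1.1 to 1.4 are in the past tense and 1.5 in the future. If the CATA answers have already been examined, tests added now are not prespecified. The documents do not settle this.

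**Conclusion.** The concern holds. As written, the CATA analysis contains no test of bread, spread or their interaction, and a significant Q cannot be credited to GF versus GC bread. That follows from the 5 df and the relabelling example alone. The practical size depends on assumed rates: across the two spread-only cases, Q is significant in roughly 31% to 96% of studies although the breads do not differ. With a bread effect equal across spreads (38% vs 58%), a direct bread test finds it in about 64% of studies against 40% for Q. The advantage reverses when the effect sits in one sample.

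This should be corrected, but it is a gap in the analysis plan and not a flaw in the design, since every participant tastes all six samples. The unstated handling of the two time points and of multiplicity is secondary.

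**What to change.** For each term, separately at each of the two time points, state three within-participant tests in section 1.5:

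- **Bread:** a paired test on each participant's GF-minus-GC count over the three spreads.
- **Spread:** a Friedman-type or permutation test on each participant's three spread totals (each 0 to 2).
- **Bread by spread:** the same type of test on the three GF-minus-GC differences.

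A GEE or mixed logistic model with a small-sample correction is an alternative for terms used often enough. Keep the six-sample Q as a secondary omnibus test, because it can be stronger when one sample stands out. State the number of tests (9 or 18 per factor), and either control the false discovery rate within each factor or call the CATA results exploratory. The exploratory label deals only with multiplicity; the bread test is still needed. If the data have already been seen, say that these tests were added afterwards.

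The cost is SAP wording and modest extra analysis, with no new data. There would be 27 to 54 tests (3 x 9 or 3 x 18), with false discoveries controlled only within each factor. Under that control over 18 tests, power for a single term falls from 64% to about 25–44% in the 38% vs 58% case. The interaction test has modest power with 20 participants.
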